Abstract

I. Title of Project: Effects of Preoxygenation with Lower Fraction of Inspired Oxygen during Induction of Anesthesia.

II. Name of Principal Investigator: [name]

III. Background:

During the induction period of general anesthesia, surgical patients are inevitably experienced a short period of apnea (no spontaneous or assisted ventilation) for endotracheal intubation or other airway manipulation. In order to minimize the risks of hypoxemia during the establishment of artificial airway, pure oxygen (oxygen partial pressure $\text{FiO}_2 = 1$) is commonly applied to the patients throughout the preoxygenation and induction period. The administration of 100% oxygen for 3 minutes in a normal subject may replace the nitrogen content in the lung cavity (de-nitrogenation) with higher alveolar concentrations of oxygen (greater than 95%). Elevation of oxygen reserve in the lung and oxygen partial pressure in the blood circulation may thus delay the development of hypoxemia (oxygen desaturation; defined as the tissue oxygen saturation below 90%) up to 10 minutes after apnea.

However, there is currently no clinical evidence indicating that preoxygenation with lower oxygen partial pressure (i.e. $\text{FiO}_2 = 0.5$ or 0.6) during the induction of anesthesia increases the incidence of hypoxemia or other complications. Most recently, two elegant large-scale clinical trials reported that the supplement of oxygen to patients with acute myocardial infarction or acute ischemic stroke did not provide any clinically beneficial effects in the prognosis of diseases. Oxygen has traditionally been recommended as a “standard” therapy for acute myocardial infarction and stroke. However, the results of these two important trials did not support the routine supplement of oxygen in these acute diseases. In addition, high concentrations of

oxygen therapy are potentially deleterious, as oxygen toxicity may result in direct tracheobronchial and alveolar damage, absorption atelectasis (lung tissue collapse) and central nervous system toxicity. In cellular levels, hyperoxia increases the production of reactive oxygen species, such as the superoxide anion, the hydroxyl radical, and hydrogen peroxide, which in turn may cause cellular apoptosis and inflammatory response. Therefore, oxygen therapy in clinical settings has been recognized as a two-edged sword and excessive oxygen supplement should be guided closely for its potential toxicity.

Currently, there is no clinical evidence that supports the routine administration of 100% oxygen prior to intubation is essential or beneficial. In the contrary, it also remains undetermined if lower fractions of inspiratory oxygen during the induction period of anesthesia may attenuate lung injury or other cellular damage derived from the oxygen toxicity. Therefore, the findings of this proposed clinical study may provide fundamental evidence for the use of different oxygen concentrations in clinical anesthesia during the induction period, and determine the effects of inspiratory oxygen concentrations on the general postoperative outcomes after general anesthesia.

IV. Purpose of the study

The aim of this study is to determine the effect of preoxygenation with pure oxygen ($\text{FiO}_2=1$) or lower partial pressure of oxygen ($\text{FiO}_2=0.6$) on the development of hypoxemia during anesthesia and major complications at 3 days after surgery. These measurements include hemodynamic parameters, acute lung injury, wound healing, pain, other systemic complications, all cause mortality, and hospital length of stay.

V. Study design: this is a randomized, open-label, observer-blind and non-inferiority clinical trial.

1. Research model: Two-group parallel interventional study.
2. Control group: Preoxygenation with 100% oxygen during the induction phase of anesthesia
3. Blind method: Open-label, observer-blind.
4. Randomization: Block randomization using randomization generator software.

VI. The number of subjects:

This study anticipates in enrolling 500 participants in each month and it will take three months to enroll a total of approximate 1500 participants.

VII. Inclusion criteria:

1. A patient who is scheduled for an elective surgery and required for anesthesia with endotracheal intubation.
2. Age of the patient is between 18 and 65 years old.
3. Patient's American Society of Anesthesiologists (ASA) Physical Status is I-III.

VIII. Exclusion criteria.

Patients who:

1. Have difficult airway for ventilation or intubation.
2. Have severe lung disease (including any acute respiratory infection).
3. Were diagnosed of coronary artery disease or myocardial infarction.
4. Have severe heart failure (NYHA Fc \geq III).
5. Have liver cirrhosis (Child-Pugh's score \geq B).

6. Have acute or chronic kidney disease (Creatinine ≥ 2 mg/dl).
7. Have severe anemia (hemoglobin ≤ 8 mg /dl).
8. Have a body mass index ≥ 35 .
9. Are currently pregnant.
10. Have not enough fasting time, intestinal obstruction or severe gastroesophageal reflux.
11. Received emergency surgery, cardiac surgery, craniotomy, or pulmonary surgery.
12. Have mental incapacitation, confusion, dementia, mental retardation, or are unable to complete the consent independently.
13. Refuse to participate in this study.

IX. Research processes:

This research study is a randomized, open-label and observer-blind trial. Patients who meet the eligibility criteria (without any exclusion criteria) and agree to join the study are randomly assigned to either high oxygen (FiO₂=1) or lower oxygen (FiO₂=0.6) group. A research assistant, who is not involved directly in patient care, will randomly assign the patients to the high oxygen (FiO₂=1) or lower oxygen (FiO₂=0.6) group.

After entering the operating room on the day of surgery, a pulse oximeter will be applied to the patient to determine the baseline levels SpO₂. Preoxygenation with different percentages of inspiratory oxygen will be administered via a face mask for 8-10 minutes before intubation of an endotracheal tube. Pulse oximeter and other standard hemodynamic parameters will be continuously monitored throughout the entire induction period. After the endotracheal tube is successfully established, the patient will be processed for maintenance of anesthesia and surgical procedure

according to the clinical practice.

X. Assessment Indicators (objective measures based on research objectives)

1. The primary endpoint of this study is the development of hypoxemia (defined as SpO₂< 92%) during the induction of anesthesia.
2. The composite secondary endpoint is the development of complications within three days after surgery, which include acute lung injury, lung collapse, pneumonia, wound infection, delayed wound healing, severe postoperative pain, prolonged hospital stay and mortality.

XI. Withdrawal from the study (Please provide a brief description of the assessment criteria and conditions for withdrawal from the study)

1. Patient or his/her family voluntarily withdraws from the study.
2. A baseline level of SpO₂ < 92% measured at operating room.
3. A Data & Security Monitoring Board (DSMB) will be established to monitor the progress of the study. This monitoring board consists of a clinical expert, a biometric expert and a human rights expert. The adverse events, number of patients who dropped out of the trial, compliance with the test, the integrity, timeliness, and the quality of the data will be closely monitored by the board members.

XII. Consent form acquisition process

The physician anesthesiologists will illustrate the purpose of study, research procedures, potential risks and follow-up of the study during the preanesthesia visit. The informed consent will then be obtained from the patient.

XIII. The expected risks, side effects and treatment

Expected risks and side effects: the administration of lower oxygen concentration (FiO₂= 0.6) during preoxygenation period may cause hypoxemia. Since tissue oxygenation will be continuously monitored throughout the anesthesia period, the development of hypoxemia during this period will be detected by the anesthesia team. Hypoxemia will be treated by the in-charge anesthesiologist according to the standard clinical guidelines, including increased concentrations of inspiratory oxygen, application of positive pressure ventilation, and increased minute ventilation.

XIV. Data Collection and Management

1. Data collection:

Medical records Questionnaire Interview Photography or photography
 Others _____

2. Person who may contact with the participants' information:

Principal Investigator Co-principal Investigator Research Assistant
 Program auditing staff Others _____

3. Data processing

Encoding identification Encryption De-linking Others _____

4. Data preservation:

The time for keeping the data: Destruction after the end of the project

Continue to save and reuse after the end of the project.
 Location of keeping the data: in the Department of Anesthesiologist Office in E-da Hospital.

■ The data in-charge person: [name], [name] (Vice-superintendent in E-da Cancer Hospital)

XV. Sample collection and samples derivative management

■ Does collect any specimen? NO.

XVI. Statistical analysis

All quantitative variables will be using a two-way RM ANOVA or unpaired t-test. And all qualitative variables will be using χ^2 test followed by the posthoc 2×2 Fisher exact test.

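### The trial is declared a non-inferiority trial, but the primary endpoint gets only tests of no difference, with no margin, confidence-interval rule or decision rule

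*Combined protocol and SAP*

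**What the plan says.** - **Design (V):** "this is a randomized, open-label, observer-blind and non-inferiority clinical trial". The word non-inferiority appears nowhere else. The aim in IV is worded as determining an effect, and IX repeats the design without the term.
- **Primary endpoint (X):** "The primary endpoint of this study is the development of hypoxemia", defined as SpO2 below 92% during induction. This is a binary outcome.
- **Analysis (XVI):** two sentences. Quantitative variables get a repeated-measures ANOVA or an unpaired t-test. Qualitative variables get a chi-square test "followed by the posthoc 2×2 Fisher exact test". Nothing further is said about the primary endpoint.
- **Sample size (VI):** 500 patients a month, so "it will take three months to enroll a total of approximate 1500 participants". No margin, event rate, alpha or power is given.
- **Expected risk (XIII):** lower oxygen "during preoxygenation period may cause hypoxemia".
- **Withdrawal (XI):** one ground is a baseline SpO2 below "92% measured at operating room". IX describes that reading after the paragraph on random assignment: "After entering the operating room on the day of surgery, a pulse oximeter will be applied to the patient".

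**The concern.** A non-inferiority trial sets out to reject the hypothesis that the new regimen is worse by at least a stated margin. Chi-square and Fisher tests instead address the hypothesis that the two arms have equal risk. Failing to reject equality is not evidence that an important excess has been ruled out.

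The natural misuse is to read p > 0.05 on hypoxemia as showing that FiO2 0.6 is non-inferior. XIII names hypoxemia as a possible harm of the lower concentration, so this is the harm the trial needs to be able to bound. With no margin in the plan, any margin used later would be chosen with the results in view.

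Two related gaps are smaller. A two-arm, yes/no endpoint already forms a 2×2 table, so XVI produces two p-values and does not say which governs. No analysis set is named, so it is unclear whether patients withdrawn under XI for low baseline SpO2 are counted.

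**Working it through.** **1. What the planned tests address.** Let d be the risk of hypoxemia with FiO2 0.6 minus the risk with FiO2 1.0, and M > 0 the margin.

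| | Null hypothesis | Evidence needed |
|---|---|---|
| Non-inferiority (V) | d ≥ M | upper confidence limit for d below M |
| Chi-square, Fisher (XVI) | d = 0 | p below a level that is not stated |

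M is undefined, so the first row cannot be evaluated from the plan. The only XVI result that would in effect imply non-inferiority is a significant one favouring FiO2 0.6.

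**2. The plan's own figure.** 500 per month × 3 months = 1500. This is an accrual projection. No power formula can reproduce it, because it would need a margin, event rate, alpha and power.

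**3. Assumptions for illustration.** 1:1 allocation (750 per arm), two-sided 5% level, Pearson chi-square without continuity correction unless stated, two-sided Fisher, Newcombe 95% interval. Event counts, true rates and the example margin are also assumed.

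Formulas, with p1 for FiO2 0.6, p2 for FiO2 1.0, p̄ the pooled rate and (l, u) the Wilson limits:
- chi-square = (p1 − p2)² / [2p̄(1 − p̄)/750]
- lower limit = d − √[(p1 − l1)² + (u2 − p2)²]
- upper limit = d + √[(u1 − p1)² + (p2 − l2)²]

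**4. Non-significant, yet a sizeable excess remains open: 16 versus 8 events.**
- p1 = 2.133%, p2 = 1.067%, d = 1.067 points, p̄ = 24/1500 = 1.6%.
- Chi-square = (8/750)² / (2 × 0.016 × 0.984/750) = 2.71, p = 0.0997. Fisher p = 0.148.
- Wilson limits: 1.317 to 3.437% and 0.541 to 2.091%.
- Upper limit = 1.067 + √(1.304² + 0.526²) = 2.47 points. Lower limit = 1.067 − √(0.816² + 1.024²) = −0.24 points.

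**5. Significant, yet inside an example margin: 15 versus 5 events.**
- p1 = 2.000%, p2 = 0.667%, d = 1.333 points, p̄ = 20/1500 = 1.333%.
- Chi-square = (10/750)² / (2 × 0.01333 × 0.98667/750) = 5.07, p = 0.024. Fisher p = 0.040.
- Wilson limits: 1.216 to 3.273% and 0.285 to 1.551%.
- Interval: 0.15 to 2.66 points, which lies below an example 3-point margin.

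The planned tests and a non-inferiority rule can therefore disagree in both directions.

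**6. How often.** Exact binomial enumeration over both arms:

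| True rates (0.6 vs 1.0) | Event | Chi-square | Fisher |
|---|---|---|---|
| 2% vs 1% | non-significant | 63.7% | 72.3% |
| equal, 0.5% to 5% | significant, favouring FiO2 0.6 | 2.2–2.5% | 0.8–1.9% |

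The second row is essentially one tail of a 5% test. A truly equal FiO2 0.6 would almost never produce the one XVI result that implies non-inferiority.

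**7. Two p-values.** At 2% versus 1%, uncorrected chi-square and Fisher fall on opposite sides of 0.05 in 8.7% of trials. With a continuity correction this falls to 0.7%. XVI does not say which chi-square is meant.

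**8. What about 1500 patients could support.** With equal true rates p and a one-sided level of 0.025, the margin detectable with 80% power is (1.960 + 0.842) × √[2p(1 − p)/750]: 1.44 points at p = 1%, 2.03 at 2% and 3.15 at 5%. Conversely, an example 2-point margin needs 778, 1540 or 3730 patients in total at those rates. Whether 1500 is enough cannot be judged until the margin and control rate are stated.

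**The case against.** The best counter-argument is that the label in V is the slip. Non-inferiority is mentioned once, IV and IX describe a comparison without it, and XVI fits that reading. This is plausible, but it leaves V in conflict with the rest of the plan, and correcting V is then the remedy.

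Four narrower points have some force.
- **Continuity correction.** It changes the chi-square figures: 16 versus 8 gives p = 0.150, the 63.7% becomes 73.0%, and disagreement between the tests falls from 8.7% to 0.7%. The two-test gap is therefore minor. The main argument is unaffected.
- **Scope of the XVI sentence.** It covers all qualitative variables. For one with more than two categories, such as ASA class, a chi-square test followed by 2×2 comparisons is sensible. For the primary endpoint it is loose wording.
- **Baseline withdrawals.** The time of randomization is not stated, so the order is inferred from IX. The baseline reading precedes the study gas, so the assigned gas cannot have caused these withdrawals, and no bias has been quantified. What stands is that their handling is unspecified.
- **Direction of risk.** XIII discloses a possible harm rather than predicting a result, and the Background (III) says no clinical evidence shows an increase.

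That XVI is merely brief is not a defence. It shows no redaction, and a confidence interval added later supports no non-inferiority decision without a margin fixed in advance.

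**Conclusion.** The concern holds and must be fixed. Followed exactly, XVI gives a p-value for a difference, which does not answer the question V declares. This follows from the wording of V, X and XVI and rests on no assumed rate.

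The size is illustrative only, because the documents give no event rates, allocation ratio, alpha or margin. At an assumed 750 per arm and a two-sided 5% level, a true doubling from 1% to 2% would go undetected in roughly two-thirds to three-quarters of trials. Each of those non-significant results could be misread as non-inferiority. The test-choice and analysis-set gaps are secondary and do not carry the conclusion.

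**What to change.** **If non-inferiority is intended:**
- In XVI, make the primary analysis a two-sided 95% confidence interval for the risk difference in hypoxemia, FiO2 0.6 minus FiO2 1.0. Name one method (Newcombe or Farrington-Manning) and state alpha and sidedness.
- Conclude non-inferiority only if the upper limit is below a margin in percentage points that is clinically justified and fixed before data are seen.
- Name the analysis set, for example all randomized patients as randomized, with a per-protocol set in support. State whether patients withdrawn for baseline SpO2 below 92% are counted, and report them by arm.
- Keep one named test of difference, as supportive only.
- In VI, state the power that about 1500 patients give for that margin and an assumed control rate. Do not choose the margin to fit the accrual total.

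**If it is not intended:** correct V, name the one governing test in XVI, and state that a non-significant result will not be read as non-inferiority.

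**Cost:** the first route needs protocol and SAP wording, a clinical justification of the margin and a power statement. It may show that power is modest, which should then be said. The second route takes little more than a line but gives up the non-inferiority claim.

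### The primary hypoxemia comparison leaves out the baseline SpO2 already recorded; prespecified adjustment would be a low-cost gain in precision, modest at best

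*Combined protocol and SAP*

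**What the plan says.** - **Baseline reading.** Section IX has an oximeter applied when the patient enters the operating room: "a pulse oximeter will be applied to the patient to determine the baseline levels". Face-mask preoxygenation for 8 to 10 minutes comes next. Random assignment is described earlier in the same section; its exact timing is not given.
- **Only stated use of the reading.** Section XI, item 2 lists as a withdrawal condition: "A baseline level of SpO₂ < 92% measured at operating room".
- **Primary endpoint.** Section X: "The primary endpoint of this study is the development of hypoxemia (defined as SpO₂< 92%) during the induction of anesthesia".
- **Analysis.** Section XVI has two sentences. The one that covers a binary endpoint is: "all qualitative variables will be using χ^2 test followed by the posthoc 2×2 Fisher exact test". The other, "All quantitative variables will be using a two-way RM ANOVA or unpaired t-test", does not apply to it. No covariate or stratification factor is named for any endpoint.
- **Randomisation and size.** Section V gives block randomisation without stratification. Section VI says "it will take three months to enroll a total of approximate 1500 participants".

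**The concern.** The trial collects, before treatment, the same quantity on which its primary event is defined. Patients lower on that scale have less distance to fall before they count as hypoxemic, so the reading is a natural candidate for a prognostic covariate. Because randomisation is not stratified on it, it is balanced between arms only by chance, and the planned analysis would carry any imbalance straight into the comparison.

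Two things are at stake, both limited. One is some precision in the estimated difference in hypoxemia rates. The other is protection against an unlucky baseline split in a trial whose conclusion is to be one of non-inferiority. Naming the covariate in advance also removes any later choice between a crude and an adjusted result, which is worth having in an open-label trial.

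**Working it through.** **The plan's own figure.** 500 per month × 3 months = 1,500, which matches section VI. This is accrual arithmetic. No alpha, power, margin or expected rate is stated, so there is no power calculation to reproduce.

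**Assumed inputs (none is in the documents).**
- Equal allocation, 750 per arm.
- Baseline SpO2 in whole points from 92 to 100, drawn from a normal with mean 97.8 and SD 1.2 or 1.6. After rounding and truncation the SD is 1.20 or 1.52.
- Log-odds of hypoxemia falling by b = 0.3, 0.5 or 0.8 per point of baseline.
- Overall event rate p = 1%, 3% or 6%, the same in both arms.

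**Formulas.**
- Crude variance of the risk difference: 2p(1−p)/750.
- Adjusted (standardised) variance: crude variance × (1 − R²), where R² = Var(E[Y | baseline]) / [p(1−p)].
- Equivalent sample size: 1,500/(1 − R²).
- 95% half-width: 1.96 × √variance.

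**Variance reduction, R² (SD 1.2 to SD 1.6).**

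| Event rate | b = 0.3 | b = 0.5 | b = 0.8 |
|---|---|---|---|
| 1% | 0.1 to 0.3% | 0.5 to 0.9% | 1.5 to 3.2% |
| 3% | 0.4 to 0.7% | 1.3 to 2.3% | 3.8 to 7.3% |
| 6% | 0.8 to 1.4% | 2.3 to 4.1% | 6.4 to 11.2% |

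**What this means for the interval.**
- Middle case (3%, b = 0.5, SD 1.6): crude half-width 1.96 × √(2 × 0.03 × 0.97/750) = 1.73 points. Adjusted: 1.73 × √(1 − 0.023) = 1.71. Equivalent size 1,500/0.977 ≈ 1,535.
- Most favourable cell (6%, b = 0.8, SD 1.6): 2.40 points becomes 2.40 × √(1 − 0.112) = 2.27. Equivalent size 1,500/0.888 ≈ 1,689.
- No association (b = 0): R² = 0 and nothing is gained.

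**Check by simulation.** With mean 97.5 and SD 1.5, 6,000 simulated trials per scenario were analysed by logistic regression and g-computation.

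| Event rate | Odds ratio per point lower | Formula | Simulation |
|---|---|---|---|
| 2% | 1.5 | 0.9% | 0.8% |
| 5% | 1.5 | 2.0% | 2.1% |
| 2% | 2.0 | 3.2% | 3.9% |
| 5% | 2.0 | 6.5% | 5.7% |

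On a wider set of assumptions the reduction reaches 31%, but only with an odds ratio of 3 per point, a 10% event rate and SD 2.0 together.

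**Chance imbalance.** The SE of the difference in mean baseline between arms is SD × √(2/750), that is 0.062 or 0.078 points. A 2-SE imbalance moves the crude risk difference by about 2 × SE × b × p(1−p)(1−R²).
- Low end (3%, b = 0.3, SD 1.2): 0.124 × 0.3 × 0.0291 × 0.996 = 0.11 percentage points.
- High end (6%, b = 0.8, SD 1.6): 0.157 × 0.8 × 0.0564 × 0.888 = 0.63 percentage points.

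The corresponding crude half-widths are 1.73 and 2.40 points.

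**Patients near the threshold.** Under these assumptions, about 0 to 5 of 1,500 patients would have a reading of 92 or 93.

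**The case against.** The strongest reply is that nothing is broken. An unadjusted comparison of randomised arms is valid, and adjustment is optional. That stands. A reader might infer from the shared 92% threshold that the planned test is biased or wrong; the documents do not support this.

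A reader might also infer that baseline must predict the endpoint strongly because both are SpO2 readings. The documents do not show it. Eight to ten minutes of mask oxygen come between baseline and intubation, the background section attributes delayed desaturation to oxygen reserve in the lung, and the baseline range is cut at 92 by the withdrawal rule and capped at 100. Nor can the case rest on patients who enter at 92 or 93%, since there would be very few of them. A gain worth well over 100 patients arises, in the table above, only with the steepest slope, the wider SD and a 3 or 6% event rate together.

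Third, it is tempting to say that adjustment narrows the interval on which non-inferiority is judged. The plan has no margin and no confidence interval, so that interval does not yet exist. Supplying it matters more than refining it.

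Finally, two practical objections to the method are fair. A logistic coefficient is a conditional odds ratio, so the model has to be standardised to give a marginal risk difference. Few events would also strain it: 1,500 × 1% is 15 events, against 45 at 3% and 90 at 6%. Both can be met in the wording of the plan.

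**Conclusion.** The point holds as an efficiency suggestion of low severity. Sections IX, X and XVI together show that a pre-treatment reading on the endpoint's own scale is collected and then left out of the primary analysis. Using it would cost little and would guard against chance imbalance.

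The gain is modest and conditional: a variance reduction of about 0.1 to 3% at a 1% event rate and 0.4 to 11% at 3 to 6%, going to zero as the association weakens. Every one of these figures rests on the assumed distribution, slope and event rate. The direction is secure, because a correctly standardised analysis should not lose precision materially at this sample size; the amount is not. The missing margin and interval, and the undefined analysis population, are more consequential gaps.

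**What to change.** Add to section XVI, in substance:

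*The primary risk difference and its two-sided 95% confidence interval will be estimated by logistic regression on arm and continuous baseline SpO2, standardised by g-computation over the prespecified primary analysis population, with robust or bootstrap standard errors. The unadjusted risk difference and its interval will be reported as a sensitivity analysis, and will be the primary result if events are too few to fit the model.*

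State in advance what triggers the fallback, for example separation or failure to converge.

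Define the primary analysis population in the same place. It cannot simply be all randomised patients while section XI, item 2 withdraws those with SpO2 below "92% measured at operating room". Section IX describes assignment before that reading, so some patients may be randomised and then withdrawn without an outcome. The two passages need to be reconciled and the handling of such patients stated.

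**Cost.** A few sentences in the plan and slightly more analysis work. The covariate is already collected, so no new data are needed. The downside is that the gain may prove negligible.

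### No use of baseline is specified for quantitative variables, although SpO₂ is read before preoxygenation is described

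*Combined protocol and SAP*

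**What the plan says.** Section XVI states: "All quantitative variables will be using a two-way RM ANOVA or unpaired t-test". It does not say which variable gets which test, what the two ANOVA factors are, which time points enter, or which term carries the treatment comparison. No covariate, change score or baseline term is named anywhere in the document. Qualitative variables get a chi-square test "followed by the posthoc 2×2 Fisher exact test", also without a baseline term.

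Section IX has a pre-treatment reading: "a pulse oximeter will be applied to the patient to determine the baseline levels" of SpO₂. The next sentence describes the intervention: "Preoxygenation with different percentages of inspiratory oxygen will be administered via a face mask for 8-10 minutes". Then: "Pulse oximeter and other standard hemodynamic parameters will be continuously monitored throughout the entire induction period". Section XI gives the only stated use of the baseline reading, withdrawal of patients whose SpO₂ is below "92% measured at operating room".

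Section IV lists what is to be measured: "These measurements include hemodynamic parameters, acute lung injury, wound healing, pain, other systemic complications, all cause mortality, and hospital length of stay". Section X makes the main outcome binary: "The primary endpoint of this study is the development of hypoxemia", defined by an SpO₂ threshold. The composite secondary endpoint is binary as worded.

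**The concern.** If serial SpO₂ or hemodynamics are compared as quantities, Section XVI leaves four possible analyses, and each is weaker than a baseline-adjusted one:

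- **Unpaired t-test on a later value.** Valid under randomization, but it discards the baseline information.
- **RM ANOVA on later values only.** The same loss.
- **RM ANOVA with baseline as a time level, group main effect tested.** A pre-treatment difference with expectation zero is averaged into the estimate, which shrinks it. In a trial framed as non-inferiority, shrinkage toward zero makes the arms look more alike.
- **RM ANOVA with baseline as a time level, group-by-time interaction tested.** Not diluted, but with one baseline and one later reading it is a change-from-baseline test, which is less precise than ANCOVA.

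Because the plan does not choose among these, the choice could be made after the data are seen. At stake are the precision and interpretation of supportive comparisons, not the main conclusion.

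**Working it through.** The documents give no figure on this point to reproduce. The sample size of about 1500 is the accrual product 500 × 3 and is not affected. The baseline-outcome correlation ρ, the SDs and the share of readings at 100% are not given, so all are assumed below.

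**1. t-test against ANCOVA, no ceiling.** Large-sample variance ratio (ANCOVA/t-test) = 1 − ρ²; CI-width ratio = √(1 − ρ²). The power column takes a t-test with 80% power as an arbitrary reference.

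| ρ | 1 − ρ² | Variance cut | CI-width cut | ANCOVA power |
|---|---|---|---|---|
| 0.1 | 0.99 | 1% | 0.5% | 80.4% |
| 0.3 | 0.91 | 9% | 4.6% | 83.6% |
| 0.5 | 0.75 | 25% | 13.4% | 89.9% |

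Simulated trials of 1500 patients (3000 runs, no ceiling) under assumed 1:1 and 2:1 allocation gave variance ratios of 0.91 and 0.90 at ρ = 0.3, and 0.75 and 0.74 at ρ = 0.5. ANCOVA type I error was 0.048 to 0.053.

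**2. The same comparison with SpO₂ capped.** Simulation with 4,000,000 draws: latent bivariate normal, both SDs 1.5, baseline mean 97.5, values rounded to 1% and capped at 100%, baseline below 92% removed. The rounding boundary of 91.5 lies (97.5 − 91.5)/1.5 = 4 SD below the mean, so almost nobody is removed. The variance cut is the square of the observed correlation.

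| Later readings at 100% | Observed correlation (latent ρ 0.1, 0.3, 0.5) | Variance cut | ANCOVA power |
|---|---|---|---|
| 50% | 0.086, 0.262, 0.438 | 0.7%, 7%, 19% | 80.3%, 82.7%, 87.6% |
| 90% | 0.057, 0.173, 0.290 | 0.3%, 3%, 8% | 80.1%, 81.2%, 83.3% |

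If the boundary instead lies 2 SD below the baseline mean (2.3% withdrawn), the variance ratios are 0.993, 0.942, 0.839 with half at 100%, a cut of 0.7%, 6% or 16%. With 90% at 100% they are 0.997, 0.977, 0.942, a cut of 0.3%, 2% or 6%.

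**3. RM ANOVA, baseline among k time levels, group main effect.** The expected baseline difference is 0, so the estimate is (0 + sum of the k − 1 later differences)/k = (k − 1)/k × the average later difference. For k = 2, 4, 6 this is 1/2, 3/4, 5/6, or 50%, 75%, 83%. If the effect varies over time, the fraction applies to its post-baseline average.

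**4. RM ANOVA, baseline and one later reading, group-by-time interaction.** With equal SDs and no ceiling, the change score has relative variance 2(1 − ρ) against 1 − ρ² for ANCOVA. The ratio is 2/(1 + ρ):

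- ρ = 0.1: 2/1.1 = 1.82; power 55.1%
- ρ = 0.3: 2/1.3 = 1.54; power 65.8%
- ρ = 0.5: 2/1.5 = 1.33; power 80.0%, equal to the t-test because 2(1 − 0.5) = 1

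The power reference is that of step 1. With half of later readings at 100% the ratios are 2.7, 2.3 and 2.1: the cap narrows the spread of the later reading, while the whole baseline value is still subtracted.

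**The case against.** The strongest case against is that no variable in the document clearly meets both conditions, a planned quantitative outcome and a recorded pre-treatment value. SpO₂ has a baseline, but its only defined outcome role is the binary endpoint. Hemodynamics are listed as measurements, but no pre-treatment value is described. Length of stay has no baseline. This is partly answered. Naming RM ANOVA implies some serial quantitative outcome, and Section IX groups the pulse oximeter with the other hemodynamic parameters, so serial SpO₂ is a plausible candidate. The document does not confirm it, and the point remains conditional.

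Other objections stand as limits on weight:

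- Against the t-test this is a matter of efficiency, and under a heavy ceiling the gain is a few percent or less.
- The 50% to 83% dilution needs both baseline as a time level and inference on the main effect.
- The change-score ratios apply to exactly two readings. With several later times the interaction has multiple degrees of freedom, and those ratios do not carry over directly.
- A two-way RM ANOVA may already include baseline as a level, so the text supports only that no use is specified, not that baseline will be ignored.
- For SpO₂ mostly at 100%, a mean difference, adjusted or not, may be a poor summary.

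The omission is also part of a wider lack of detail in Section XVI. It still merits its own line, because a better method is available for a value already measured.

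**Conclusion.** The concern holds, with minor weight. Section XVI specifies no use of baseline for quantitative variables, and the one stated use of the baseline SpO₂ reading is the withdrawal rule. The binary primary endpoint, the binary composite and the sample size are untouched.

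For supportive quantitative outcomes with a pre-treatment value, baseline adjustment gives an interval at least as narrow in large samples as the t-test or the change-from-baseline contrast, given equal allocation or a common baseline slope (the allocation ratio is not stated). The gain over the t-test depends wholly on an unknown correlation and, for SpO₂, on how many readings sit at 100%; it could be negligible. The firmer benefit is naming the contrast in advance, which excludes the diluted main effect and the noisier change score.

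**What to change.** In Section XVI, list each quantitative outcome with its time points and state whether a pre-treatment value is recorded. Then:

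- For a single post-baseline value with a recorded baseline, use ANCOVA.
- For repeated post-baseline values, use a mixed model with baseline as a covariate; a constrained longitudinal model is an acceptable equivalent.
- Name the treatment contrast (a stated time point or the post-baseline average) and report the adjusted mean difference with its 95% CI.
- Keep the t-test, or another stated method, for outcomes without a baseline, such as length of stay.

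The cost is SAP wording and slightly more programming, with no additional patients. SpO₂ is already read at baseline, but the value must be kept as study data, which the document does not state. For hemodynamics the change applies only if a pre-treatment value is recorded.
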